1. INTRODUCTION

1.1 Literature Review

Colorectal cancer is the second leading cause of cancer-related deaths worldwide. It is estimated that 10% of cancer mortality is attributed to malignant neoplasms of the colon and rectum [1]. More specifically, in the United States alone, 53,200 colorectal cancer deaths were reported [2].

The current treatment of choice for locally advanced rectal cancer (Stage II/ III) is the combination of neoadjuvant chemoradiation followed by radical surgical resection based on the principles of total mesorectal excision (TME) after a 8-12 weeks period [3]. Therapy is usually completed with the administration of adjuvant chemotherapy based on oxaliplatin and fluoropyrimidines. This combined approach allowed the reduction of local recurrence at levels around 5%. Despite the impressive results in local control, the same was not confirmed for the long-term, overall survival. Possible explanations to that are: a) the compliance and completion of the treatment schemes during the postoperative period were low and b) there was a delay in the administration of adjuvant chemotherapy; both could lead to subclinical metastatic disease progression [4].

On the basis of achieving both goals, (i.e., local control through neoadjuvant radiotherapy and metastatic disease control through systemic chemotherapy) the administration of the two therapies in the preoperative period was proposed, in the form of combined or total neoadjuvant therapy [1, 5–8].

Additional theoretical benefits of total neoadjuvant therapy are faster defunctioning stoma reversal, as well as the possibility of a more accurate evaluation of the tumor biological behavior, thus enabling a safer staging for patients who would be candidates for a watch and wait protocol [1–3, 5–12]. Furthermore, for patients who will eventually undergo surgery, total neoadjuvant therapy could probably increase R0 resection and sphincter-preservation rates [3, 5, 8– 10, 12].

However, many researchers question the safety and efficacy of total neoadjuvant therapy [7, 13]. First, the administration of neoadjuvant chemotherapy significantly increases the risk of

severe toxicity from cytotoxic agents [14]. At the same time, according to the results of one of the largest prospective randomized trials, the addition of neoadjuvant chemotherapy into the treatment algorithm did not offer any advantage in the pathological response, 5-year overall and disease-free survival rates [15]. Finally, there is considerable heterogeneity in the current literature, most likely reflecting the different schemes used in different trials regarding the radiotherapy regimen, the chemotherapy regimen as well as the sequence of each one in each protocol [16].

We believe it is difficult to interpret any differences in results when multiple parameters have been changed in a comparative trial [17]. For this reason, when testing our current standard neoadjuvant protocol to the new trend of total neoadjuvant therapy we decided to keep the same scheme and timing for the experimental group also, and the only parameter which is different is the use of the classic chemotherapy scheme during the waiting period following chemoradiation and before surgery [18].

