2. OBJECTIVE

2.1 Description of the proposed project

The purpose of this protocol is to compare neoadjuvant chemoradiation plus consolidation chemotherapy before surgical resection with the standard neoadjuvant chemoradiation followed by surgical resection and adjuvant chemotherapy in patients with rectal cancer.

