3.4 Study Arms

In this study there will be two arms [5, 10]. Patients that are randomized in the first arm will receive neoadjuvant chemoradiotherapy and consolidation chemotherapy and then undergo surgical resection of the tumor. In the second arm, patients will receive the standard long-course neoadjuvant chemoradiotherapy regimen and then undergo tumor resection. The treatment will be completed with adjuvant chemotherapy. In both groups, surgery will follow the principles of total mesorectal excision (TME).

The control group will receive the standard 5-week neoadjuvant chemoradiotherapy regimen. Six weeks after completion the patient will be re-staged with rectal MRI and depending on the response will be operated (TME): immediately in case of non-response (mrTRG 5) or after an additional 6-week delay (overall 12 weeks after the end of chemoradiotherapy) in case of partial response (mrTRG 2-4). Adjuvant chemotherapy will be, also, administered.

The experimental group will receive the standard 5-week neoadjuvant chemoradiotherapy (CRT). Thereafter, all patients will commence consolidation chemotherapy. At the 6th week after the end of CRT, patients will undergo MRI re-staging: In case of non-response (mrTRG 5) they will be submitted immediately to surgery, and, subsequently, excluded from the trial. In case of response (mrTRG 2-4) they will receive consolidation chemotherapy for the whole waiting period between the end of CRT and surgery - 12 weeks.

The following interventions will be introduced:

Neoadjuvant Chemoradiotherapy. 5-week neoadjuvant radiotherapy regimen (28 x 1.8 Gy) combined with Capecitabine (bid 800 mg/m², twice daily, on days 1-33-38)

Consolidation Chemotherapy. CAPOX (Capecitabine bid 1000 mg/m² and Oxaliplatin 130 mg/m², day 1, every 3 weeks) or alternatively FOLFOX

Adjuvant Chemotherapy. 8 cycles of CAPOX (Capecitabine bid 1000 mg/m², twice daily, day 1-14, every 3 weeks and Oxaliplatin 130 mg/m², day 1, every 3 weeks) or alternatively, 12 cycles of folinate, fluorouracil and oxaliplatin (FOLFOX)

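### Section 1.1 claims that only waiting-period chemotherapy differs between the arms, but adjuvant chemotherapy is tied to the control arm, so a DFS difference cannot be credited to consolidation alone

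*Protocol*

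**What the plan says.** Section 1.1 sets out a principle and then applies it. The principle is: "We believe it is difficult to interpret any differences in results when multiple parameters have been changed in a comparative trial". The application is that "we decided to keep the same scheme and timing for the experimental group also", and that "the only parameter which is different is the use of the classic chemotherapy scheme during the waiting period following chemoradiation and before surgery". The sentence opens by framing the trial as a test of the centre's existing neoadjuvant protocol against total neoadjuvant therapy.

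The objective in 2.1 sets "neoadjuvant chemoradiation plus consolidation chemotherapy before surgical resection" against the comparator, "with the standard neoadjuvant chemoradiation followed by surgical resection and adjuvant chemotherapy in patients with rectal cancer". Adjuvant chemotherapy appears on the control side only.

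Section 3.4 describes each arm twice. For the experimental arm: "Patients that are randomized in the first arm will receive neoadjuvant chemoradiotherapy and consolidation chemotherapy and then undergo surgical resection of the tumor". Its later, longer paragraph also ends at surgery. The control paragraph closes by adding adjuvant chemotherapy. Two further places mention adjuvant treatment without naming an arm: the sentence "The treatment will be completed with adjuvant chemotherapy", which directly follows the description of the second arm, and the intervention list, which gives 8 cycles of CAPOX or 12 of FOLFOX.

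The primary endpoint (3.7) is DFS with a time frame of three years postoperatively.

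**The concern.** Section 1.1 offers the single-parameter design as the reason the results will be interpretable. If adjuvant chemotherapy goes to the control arm only, the arms differ in two systemic components: the experimental arm gains consolidation and lacks adjuvant treatment, and the control arm has the reverse.

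DFS at three years is observed well after the adjuvant period and can be affected by adjuvant treatment. A difference in DFS, or the lack of one, would then reflect the two sequences as wholes. A favourable result could not be reported as the effect of adding consolidation. A null result could not be read as consolidation having no effect, because a benefit could be offset by the missing adjuvant treatment. The design would lack the property that 1.1 gives as its justification.

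**Working it through.** The protocol has no figure to reproduce on this point, so the check is a comparison of its statements.

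**Step 1. What each place implies for the experimental arm.**

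- 1.1, design rationale: one difference only, chemotherapy in the waiting period. Taken over the whole treatment course, this requires adjuvant treatment to be the same in both arms.
- 1.1, background: "the administration of the two therapies in the preoperative period was proposed, in the form of combined or total neoadjuvant therapy". Systemic treatment is moved ahead of surgery, which fits an experimental arm without an adjuvant phase.
- 2.1: adjuvant chemotherapy is named for the control strategy and not for the experimental one.
- 3.4, opening paragraph: the experimental arm ends at surgery. The adjuvant sentence names no arm, but it follows the second-arm sentence, and the next sentence turns explicitly to both groups.
- 3.4, detailed paragraphs: adjuvant treatment is added for control, with no counterpart for experimental.
- 3.4, intervention list: a regimen and cycle counts, with no arm.

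No place states that the experimental arm receives adjuvant chemotherapy, and no place states that it does not.

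**Step 2. Count the differing components under each reading.**

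- Control-only: consolidation (experimental yes, control no) and adjuvant (experimental no, control yes). Two components differ, and the 1.1 statement can be true only up to surgery.
- Both arms: consolidation only. One component differs. The 1.1 statement can stand on this point, but 2.1 and 3.4 omit part of the experimental treatment.

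The order of the sentences in 3.4, the objective and the background all favour control-only. The both-arms reading rests on the entries that name no arm and on the 1.1 sentence itself.

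**Step 3. Illustrative exposure only.** Section 3.4 gives 12 weeks of consolidation and a 3-week CAPOX cycle but no number of consolidation cycles. The most that fits is 12 / 3 = 4, an inferred upper bound for patients treated through the full wait.

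- Control-only: at most 4 cycles against 8, a ratio of at most 4 / 8 = 0.5.
- Both arms: at most 4 + 8 = 12 against 8, a ratio of at most 12 / 8 = 1.5.

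These ratios describe planned cycles and say nothing about the size of any DFS effect. For FOLFOX neither a consolidation count nor a cycle length is given, so no figure follows.

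**The case against.** The strongest reply is that the 1.1 sentence concerns the neoadjuvant phase. It opens by naming the existing neoadjuvant protocol as the thing under test, it speaks of keeping scheme and timing the same, and the paragraph before it criticises trials that vary the radiotherapy regimen, the chemotherapy regimen and their sequence. Read in that frame, it says that chemoradiation and the waiting interval are held constant while chemotherapy is added in the interval. That is compatible with control-only adjuvant treatment, so a flat contradiction is not shown.

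This much stands: the sentence is loose rather than plainly false. It does not remove the point. The reason given is about differences in results generally, and the result that matters is DFS three years after surgery. A statement true only up to surgery cannot support the interpretation of that endpoint.

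A second reply is that comparing whole strategies is legitimate and that the objective is worded as such a comparison. That stands in full. The objection here is only to the claim in 1.1 to have isolated one parameter.

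A reader might also infer that the protocol leaves the question of adjuvant treatment wholly open. It does not: the text leans clearly to control-only. It never says so for the experimental arm, however, and that remains a gap.

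**Conclusion.** The point holds in a limited form. On the better-supported reading two components differ where 1.1 claims one, and a DFS difference at three years cannot be attributed to consolidation alone. This rests on taking adjuvant chemotherapy as control-only, which the protocol implies but does not state. If both arms receive it, the attribution problem from adjuvant treatment disappears, and what remains is an incomplete description of the experimental arm in 2.1 and 3.4.

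Two stronger conclusions are tempting and unsupported. One is that the trial is confounded or its comparison invalid: randomisation supports a valid comparison of the two strategies under either reading. The other is that the protocol expressly withholds adjuvant chemotherapy from experimental patients: it is silent.

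The size is one extra differing component. Its effect on DFS cannot be derived from the protocol. The matter should be corrected, because it determines what the trial may conclude, and treatment assignment belongs in the protocol rather than in an analysis plan.

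**What to change.** Reconcile 1.1, 2.1 and 3.4 by stating for each arm whether adjuvant chemotherapy is given, and name the arm in the 3.4 sentence and in the intervention-list entry that now name none. The sponsor decides which version applies; no view is taken here on which treatment is right.

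- If control-only: limit the 1.1 sentence to the chemoradiation scheme and waiting period. Possible wording: The chemoradiation scheme and the waiting period are the same in both arms; the trial compares chemoradiation, consolidation and surgery with chemoradiation, surgery and adjuvant chemotherapy, and does not isolate the effect of consolidation. Restrict the DFS conclusion in the same way.
- If both arms: add adjuvant chemotherapy to the experimental strategy in 2.1 and to the experimental-arm descriptions in 3.4.

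The cost is a text amendment, with no change to sample size or data collection. The downside in the control-only case is a narrower conclusion: the trial gives up any claim about consolidation by itself.

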2. OBJECTIVE

2.1 Description of the proposed project

The purpose of this protocol is to compare neoadjuvant chemoradiation plus consolidation chemotherapy before surgical resection with the standard neoadjuvant chemoradiation followed by surgical resection and adjuvant chemotherapy in patients with rectal cancer.

3. MATERIAL AND METHODS

3.1 Population

The sample will consist of males and females aged 18 to 80 years.

3.2 Diseases

The study will include patients with rectal cancer that will meet the current criteria for neoadjuvant chemoradiotherapy, and surgical resection based on the principles of total mesorectal excision (TME).

3.3 Inclusion / Exclusion Criteria

Inclusion criteria are the following [10]:

- Histologically confirmed rectal adenocarcinoma
- cT3, cT4, threatened CRM / MRF, EMVI (+), $\geq N1$
- Multidisciplinary tumor board decision for neoadjuvant treatment
- Tumor distance from the anal verge ≤ 15 cm based on endoscopy or magnetic resonance imaging
- Patient 18 to 80 years old
- General health condition status WHO 0-1
- Absence of co-morbidities that may affect treatment
- Neutrophils $> 1,500$ / mm³, platelets $> 100,000$ / mm³, hemoglobin > 10 g / dL, normal creatinine, and creatinine clearance > 50 mL / min
- Signed informed consent of the patient

Exclusion criteria are the following:

- Distant metastases
- Non-resectable cancer
- Contraindications for the administration of chemotherapy
- Previous pelvic radiotherapy or chemotherapy

- History of inflammatory bowel disorders
- History of angina, acute myocardial infarction or heart failure
- Active sepsis or systemic infection
- Untreated physical and mental disability
- Synchronous malignancy
- Pregnancy or breast-feeding
- Lack of compliance with the protocol process
- Non-granting of signed informed consent

3.4 Study Arms

In this study there will be two arms [5, 10]. Patients that are randomized in the first arm will receive neoadjuvant chemoradiotherapy and consolidation chemotherapy and then undergo surgical resection of the tumor. In the second arm, patients will receive the standard long-course neoadjuvant chemoradiotherapy regimen and then undergo tumor resection. The treatment will be completed with adjuvant chemotherapy. In both groups, surgery will follow the principles of total mesorectal excision (TME).

The control group will receive the standard 5-week neoadjuvant chemoradiotherapy regimen. Six weeks after completion the patient will be re-staged with rectal MRI and depending on the response will be operated (TME): immediately in case of non-response (mrTRG 5) or after an additional 6-week delay (overall 12 weeks after the end of chemoradiotherapy) in case of partial response (mrTRG 2-4). Adjuvant chemotherapy will be, also, administered.

The experimental group will receive the standard 5-week neoadjuvant chemoradiotherapy (CRT). Thereafter, all patients will commence consolidation chemotherapy. At the 6th week after the end of CRT, patients will undergo MRI re-staging: In case of non-response (mrTRG 5) they will be submitted immediately to surgery, and, subsequently, excluded from the trial. In case of response (mrTRG 2-4) they will receive consolidation chemotherapy for the whole waiting period between the end of CRT and surgery - 12 weeks.

The following interventions will be introduced:

Neoadjuvant Chemoradiotherapy. 5-week neoadjuvant radiotherapy regimen (28 x 1.8 Gy) combined with Capecitabine (bid 800 mg/m², twice daily, on days 1-33-38)

Consolidation Chemotherapy. CAPOX (Capecitabine bid 1000 mg/m² and Oxaliplatin 130 mg/m², day 1, every 3 weeks) or alternatively FOLFOX

Adjuvant Chemotherapy. 8 cycles of CAPOX (Capecitabine bid 1000 mg/m², twice daily, day 1-14, every 3 weeks and Oxaliplatin 130 mg/m², day 1, every 3 weeks) or alternatively, 12 cycles of folinate, fluorouracil and oxaliplatin (FOLFOX)

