3.7 Primary endpoint

Disease Free Survival. Occurrence of Disease Free Survival. If such an episode occurs, then it will be defined as=1 'YES' If such an episode does not occur, then it will be defined as=0 'NO'. [Time Frame: 3 years postoperatively]

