3.8 Secondary endpoints

Secondary endpoints of the present study are:

Complete Pathological Response. Occurrence of Complete Pathological Response. If such an episode occurs, then it will be defined as=1 'YES' If such an episode does not occur, then it will be defined as=0 'NO'. [Time Frame: 1 month postoperatively]

Postoperative Complications. Occurrence of postoperative complications based on the Clavien Dindo Classification [20]. If such an episode occurs, then it will be defined as=1 'YES' If such an episode does not occur, then it will be defined as=0 'NO'. [Time Frame: 1 month postoperatively]

Length of Hospital Stay. Postoperative time that the patient can be safely discharged. Measurement unit: days. The patient will be discharged, when it is ensured that is medically safe

to be released. In particular, as the exit time of the patient, will be regarded the time that the patient will fulfil the Clinical Discharge Criteria. [Time Frame: Maximum time frame 39 days postoperatively]

Readmission. Occurrence of postoperative readmission. If such an episode occurs, then it will be defined as=1 'YES' If such an episode does not occur, then it will be defined as=0 'NO'. [Time Frame: 1 month postoperatively]

Negative Resection Margin. Occurrence of Negative Resection Margin. If such an episode occurs, then it will be defined as=1 'YES' If such an episode does not occur, then it will be defined as=0 'NO'. [Time Frame: 1 month postoperatively]

Overall Survival. Occurrence of Overall Survival. If such an episode occurs, then it will be defined as=1 'YES' If such an episode does not occur, then it will be defined as=0 'NO'. [Time Frame: 3 years postoperatively]

Chemotherapy Toxicity. Occurrence of Chemotherapy Toxicity. If such an episode occurs, then it will be defined as=1 'YES' If such an episode does not occur, then it will be defined as=0 'NO'. [Time Frame: 3 years postoperatively]

Local Recurrence. Occurrence of Local Recurrence. If such an episode occurs, then it will be defined as=1 'YES' If such an episode does not occur, then it will be defined as=0 'NO'. [Time Frame: 3 years postoperatively]

Treatment Compliance. Occurrence of Treatment Compliance. If such an episode occurs, then it will be defined as=1 'YES' If such an episode does not occur, then it will be defined as=0 'NO'. [Time Frame: 3 years postoperatively]

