3.9 Calculation of the sample size

The sample size calculation was based on the primary endpoint. According to the literature, the disease-free survival Hazard Ratio between standard practice and combined neoadjuvant therapy is 0.23 [21]. Therefore, for a prospective randomized study with alpha: 5%, power: 90% and dropout

rate: 15%, the estimated number of patients in each group is 42. A total of 84 patients will be required.

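### mrTRG 5 non-responders leave the trial in the experimental arm only, which biases DFS, OS, pathological response and margin status in that arm's favour

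*Protocol*

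**What the plan says.** Section 3.4 (Study Arms) gives both arms the same chemoradiotherapy and the same re-staging MRI at week 6.

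- **Control arm.** Surgery takes place "immediately in case of non-response (mrTRG 5) or after an additional 6-week delay" for partial responders. The paragraph then closes with "Adjuvant chemotherapy will be, also, administered". Nothing removes the mrTRG 5 patients from the trial.
- **Experimental arm.** After chemoradiotherapy, "Thereafter, all patients will commence consolidation chemotherapy". At the MRI, "In case of non-response (mrTRG 5) they will be submitted immediately to surgery, and, subsequently, excluded from the trial".

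The primary endpoint (section 3.7) is DFS at 3 years after surgery. Secondary endpoints (section 3.8) include overall survival, complete pathological response and negative resection margin. Section 3.9 states that "the estimated number of patients in each group is 42", with a single 15% dropout rate and no mention of the mrTRG 5 exclusion. Section 3.13 provides for outcomes to be recorded at 3 and 5 years but does not say that excluded patients are covered. The protocol contains no intention-to-treat statement.

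**The concern.** The same MRI result and the same surgical step lead to different trial status depending on the arm. The exclusion is made after randomisation and depends on how the patient responded. The patients removed have received part of the new strategy without responding, yet they would not count against it, while their counterparts stay in the control arm's results.

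If non-responders have a worse outlook than responders, the experimental arm is left with a selected, better group. The comparison of DFS, overall survival, pathological response and margins then favours it without any treatment effect. The other secondary endpoints also lose the protection of randomisation, although the direction of their bias is not clear.

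Two features make this worse:

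- Consolidation chemotherapy starts before the MRI, so the mrTRG grade may itself depend on allocation. Excluding mrTRG 5 patients from both arms would therefore not restore comparability.
- The trial is open-label (section 3.11). If the MRI reader knows the allocation, that reader also knows that a grade of 5 removes a patient only in the experimental arm.

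Section 1.1 says the arms are meant to differ only in chemotherapy during the waiting period. This rule adds a second difference, in who is counted.

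**Working it through.** **1. The two arms side by side (section 3.4)**

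| | Control | Experimental |
|---|---|---|
| MRI 6 weeks after chemoradiotherapy | yes | yes |
| Consolidation chemotherapy begun before the MRI | no | yes |
| mrTRG 5: immediate surgery | yes | yes |
| mrTRG 5: removed from the trial | not stated | stated |

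**2. The planned size.** Inputs from section 3.9 are HR 0.23, alpha 5%, power 90% and dropout 15%. Schoenfeld's formula, two-sided, gives 4 × (1.960 + 1.282)² / (ln 0.23)² = 42.0 / 2.16 = 19.5, so 20 events. The control event rate is not given, so 42 per group can be neither confirmed nor refuted. It is reached if the control 3-year event rate is taken as 45%: the experimental rate is then 1 − 0.55^0.23 = 12.8%, n = 20 / (0.45 + 0.128) = 35 per arm, and 35 / 0.85 gives 42. The bias below does not depend on this calculation.

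**3. Apparent effect with no true effect.** Let q be the share with mrTRG 5, and S_R and S_N the 3-year DFS in responders and non-responders. Control shows S_C = (1 − q)S_R + qS_N. The experimental arm, stripped of its non-responders, shows S_R. The apparent HR is ln(S_R) / ln(S_C). The protocol gives none of q, S_R or S_N, so all values here are assumptions. Example for q = 10%, S_R = 70%, S_N = 35%: S_C = 0.63 + 0.035 = 66.5%, and HR = 0.357 / 0.408 = 0.87.

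**4. False positives.** Simulated trials used 42 per arm, 15% random dropout, exponential times and a log-rank test at 3 years. A false win is a significant result favouring the experimental arm at two-sided 5% (nominal 2.5% in that direction). S_R is 70% throughout.

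| q | S_N | S_C | Apparent HR | False win |
|---|---|---|---|---|
| 0 | – | 70.0% | 1.00 | 2.6% |
| 5% | 50% | 69.0% | 0.96 | 3.2% |
| 5% | 35% | 68.3% | 0.93 | 3.7% |
| 10% | 60% | 69.0% | 0.96 | 3.3% |
| 10% | 35% | 66.5% | 0.87 | 5.1% |
| 15% | 35% | 64.8% | 0.82 | 6.6% |
| 20% | 35% | 63.0% | 0.77 | 7.9% |
| 20% | 20% | 60.0% | 0.70 | 13.2% |

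Repeat simulations gave 4.9 to 5.4%, 6.4% and 8.1 to 8.5% for the rows with S_N = 35% and q = 10%, 15% and 20%. In the mild rows the total two-sided error barely moves: 5.3% (q = 5%, S_N = 50%), 5.6% (q = 5%, S_N = 35%) and 5.4% (q = 10%, S_N = 60%).

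**5. A second set of assumptions.** Here the 3-year event risk is 25% in responders and 50% or 75% in non-responders, with 36 per arm (42 less 15%) and 10,000 runs.

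| q | HR, false win (risk 50%) | HR, false win (risk 75%) |
|---|---|---|
| 5% | 0.945, 3.0% | 0.895, 4.2% |
| 10% | 0.895, 4.0% | 0.807, 6.6% |
| 20% | 0.807, 6.4% | 0.668, 12.4% |
| 30% | 0.732, 7.9% | 0.563, 23.0% |

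With every randomised patient kept, the false-win rate is 2.2 to 2.8% in these scenarios.

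**6. Pathological response.** If no mrTRG 5 patient has a complete response, removing them multiplies the experimental rate by 1 / (1 − q): 1.11, 1.18 and 1.25 at q = 10%, 15% and 20%. For example, with 20% in responders and q = 10%, the whole-arm rate is 18% but 20% is reported.

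**7. Numbers left.** After 15% dropout, 42 × 0.85 = 35.7 patients remain per arm. If the exclusions come on top of that, the experimental arm keeps 35.7 × (1 − q) = 32, 30 and 29 at q = 10%, 15% and 20%. Control keeps about 36.

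**The case against.** Several points can fairly be made on the other side.

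- **Analysis sets are often defined in the SAP, which is not available here, and the sentence may only mean leaving protocol treatment.** Either is possible. But the words remove patients from the trial itself, and an SAP cannot recover follow-up that was never collected. If only discontinuation of consolidation is meant, the sentence still needs correcting.
- **Retention of control non-responders is inferred from silence.** That is so. It is nevertheless the natural reading: their surgery is described, adjuvant chemotherapy follows for the group, and no exclusion is mentioned.
- **Worse prognosis in mrTRG 5 is assumed.** This stands as a condition. The direction of bias follows only if non-responders do worse, which is plausible but not documented in the protocol.
- **The bias may be small.** This also stands. With a share near 5%, or with non-responders only slightly worse, the error rate hardly changes.
- **The pathological-response factor assumes no complete responses among mrTRG 5 patients, and the 15% dropout allowance may have been meant to cover the exclusions.** Both are fair, so the inflation factor is an upper figure if some mrTRG 5 patients do respond completely, and the loss of sample size is possible rather than established.

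These points limit the size of the bias. None removes the asymmetry in the text.

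**Conclusion.** The concern holds. As written, section 3.4 makes a response-based exclusion after randomisation in one arm only, and nothing else in the protocol keeps those patients under follow-up or excludes their control counterparts. Provided non-responders do worse than responders, DFS and overall survival are biased toward the experimental arm; pathological response and margin status are biased the same way if those results are less frequent in non-responders. The remaining secondary endpoints lose their randomised comparison without a clear direction.

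The size cannot be fixed from the protocol. Across the assumptions tried, with no true effect, the apparent DFS hazard ratio runs from 0.96 to 0.56 and the chance of a false win from about 3% to 23%, against a nominal 2.5%. It is slight at a 5% share and substantial at 20% or more. Because the bias falls on the primary endpoint and may be impossible to undo once follow-up stops, this must be fixed.

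**What to change.** Delete the clause in section 3.4 that removes experimental-arm mrTRG 5 patients from the trial. State instead that every randomised patient, including mrTRG 5 patients in both arms, is followed for all endpoints and analysed in the allocated arm (intention to treat). Say explicitly that ending consolidation and going to surgery is not withdrawal from the trial. A responders-only analysis may be kept if it is labelled exploratory.

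This leaves the clinical handling of mrTRG 5 patients as it is. The cost is a one-sentence amendment and routine follow-up of a few patients: on average 42 × q, or 2.1, 4.2 and 8.4 at shares of 5%, 10% and 20%. The estimated effect will probably be somewhat less favourable to the experimental arm. The change should be made before any such patient is lost to follow-up; those already excluded should be brought back into follow-up where consent allows.

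### Experimental-arm non-responders (mrTRG 5) are excluded from the trial after randomisation while control non-responders stay, which favours the new treatment if non-responders do worse

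*Protocol*

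**What the plan says.** Protocol section 3.4 re-stages both arms by MRI six weeks after the end of chemoradiotherapy.

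- **Experimental arm.** Consolidation begins before that MRI: "Thereafter, all patients will commence consolidation chemotherapy". For those then graded mrTRG 5, the rule is: "In case of non-response (mrTRG 5) they will be submitted immediately to surgery, and, subsequently, excluded from the trial".
- **Control arm.** The operation takes place "immediately in case of non-response (mrTRG 5) or after an additional 6-week delay", the latter for partial responders. The paragraph ends: "Adjuvant chemotherapy will be, also, administered". It makes no exception for mrTRG 5 and mentions no exclusion.

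No other section reverses the experimental-arm rule, extends it to controls, or says that the excluded patients are still followed or analysed. Section 3.7 makes three-year disease-free survival the primary endpoint. Section 3.9 states that "the estimated number of patients in each group is 42", with a 15% dropout allowance that does not mention this exclusion.

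**The concern.** Randomisation makes the arms comparable only while everyone randomised is counted. Here a subgroup defined by poor response leaves one arm and stays in the other. In the experimental arm the response is read after the assigned chemotherapy has begun, so the treatment itself can influence who is removed.

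If poor responders also relapse or die more often, the experimental arm loses some of its worst-prognosis patients and the control arm loses none. Disease-free survival then looks better under the new treatment whether or not it works. Immediate surgery for non-responders is not the problem, because both arms have it. The problem is that in one arm the change of treatment is also an exit from the trial.

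**Working it through.** **The plan's own figure.** The protocol gives a hazard ratio (HR) of 0.23, alpha 5%, power 90%, 15% dropout and 42 per group, but no control event rate. By Schoenfeld's formula, two-sided, events = 4 × (1.960 + 1.282)² / (ln 0.23)² = 19.5, so 20. If control three-year disease-free survival is taken as 55%, the experimental value is 0.55^0.23 = 0.872 and the mean event probability is (0.45 + 0.128)/2 = 0.289. That gives 20/0.289 = 69.2, so 70 in total or 35 per arm, and 35/0.85 = 41.2, so 42. The stated size is therefore reachable, and nothing below depends on its being wrong.

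**Inputs for the bias.** The 42 per arm is from section 3.9. Everything else is assumed, because the protocol does not give it:
- mrTRG 5 share s: 5%, 10% or 15%, the same in both arms
- three-year event risk p among mrTRG 5 patients: 50%, 60% or 70%
- overall three-year event risk r: 40% in both arms, so the true HR is 1.00

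**Formulas.** The experimental risk after exclusion is (r − s × p)/(1 − s), and the control risk stays at r. The apparent HR is ln(1 − experimental risk)/ln(1 − control risk). Patients removed are 42 × s. Events removed are 42 × s × p, out of 42 × 0.40 = 16.8 expected.

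Worked case, s = 0.10 and p = 0.60: (0.40 − 0.06)/0.90 = 0.378, and ln(0.622)/ln(0.600) = 0.929.

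| s, p | Patients removed | Events removed | Experimental risk left | Apparent HR | False win, all kept | False win, as written |
|---|---|---|---|---|---|---|
| 5%, 50% | 2.1 | 1.05 | 0.395 | 0.983 | 2.5% | 2.8% |
| 10%, 60% | 4.2 | 2.52 | 0.378 | 0.929 | 2.4% | 3.9% |
| 15%, 70% | 6.3 | 4.41 | 0.347 | 0.834 | 2.7% | 6.9% |
| any share, 40% | 42 × s | 42 × s × 0.40 | 0.400 | 1.000 | not run | not run |

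A false win is a significant result in favour of the experimental arm when there is no true effect (nominal 2.5%). The rates come from 40,000 simulated trials per case: 42 per arm, exponential times within grade, censoring at three years, and a log-rank test (assumed) at two-sided 5%. Simulation error is about 0.1 percentage point.

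**If consolidation lowers the experimental share.** Halve s in the experimental arm and keep overall risk at 40%. The three apparent HRs become 0.99, 0.97 and 0.92. For the last, (0.40 − 0.075 × 0.70)/0.925 = 0.376 and ln(0.624)/ln(0.600) = 0.92.

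**A second set of assumptions.** Take three-year disease-free survival of 75% outside mrTRG 5, 30-50% within it, and shares of 5-20%. The apparent HR runs from 0.95 to 0.69 and the false-win rate from 3.3% to 13.1% (8,000 simulated trials per case). For the extreme case, control disease-free survival is 0.20 × 0.30 + 0.80 × 0.75 = 0.66, and ln(0.75)/ln(0.66) = 0.69. The size moves with the inputs; the direction stays the same as long as mrTRG 5 patients do worse.

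**The case against.** **Two links are read from context.** That control mrTRG 5 patients stay in the trial rests on the absence of any exclusion together with the adjuvant chemotherapy given to that arm. That randomisation comes first rests on the description of the arms in section 3.4, because section 3.10 gives no time point. Both are the natural reading and no passage contradicts them, but neither is stated outright.

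**Exclusion need not mean that follow-up stops.** A reader might infer that outcomes of these patients will never be collected and that no analysis plan could recover them. The protocol does not say so. Exclusion could mean leaving trial treatment, the analysis set or follow-up. Section 3.13 places patients on standard monitoring, and the work is done at one hospital with patient charts, so the data may exist. This tempers the consequence. It does not remove the need to correct a sentence that, as written, takes these patients out of the trial.

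**The size is assumed.** This stands. The low case is negligible, and the high case pairs the largest share with the largest risk. The main calculation also holds the share equal across arms although consolidation may lower it.

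**Loss of numbers.** The 15% allowance is 0.15 × 42 = 6.3 patients, as many as the upper end of the exclusion. The loss is therefore not shown to be a separate power problem. The allowance deals with numbers, however, and not with selective removal from one arm.

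**The stated principle of one difference.** A reader might see a contradiction with the introduction, where "the only parameter which is different is the use of the classic chemotherapy scheme during the waiting period". That sentence concerns treatment scheme and timing, not retention in the trial, so the point does not rest on it.

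**Conclusion.** The point holds. Followed as written, section 3.4 produces a one-arm, post-randomisation exclusion based on response. It favours the experimental arm if mrTRG 5 patients do worse than the rest, and leaves the HR unbiased if they do not. Under the main assumptions (share 5-15% in both arms, mrTRG 5 risk 50-70%, overall risk 40%) a true HR of 1.00 appears as 0.98 to 0.83, with a false-win rate of about 2.8% to 6.9% against 2.5%. That is negligible at the low end and material towards the high end. The protocol should be changed because the rule is plainly worded and cheap to correct, not because a large bias has been shown.

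Two stronger readings are not supported:

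- **A much larger distortion when the treatment works.** With risks of 40% and 30% (true HR 0.70), one can reach apparent values of 0.67, 0.61 and 0.51. Those figures assume that mrTRG 5 patients get no benefit. Applying the same HR to them gives about 0.69, 0.65 and 0.57. The protocol supports neither choice.
- **Wider faults in the same rules.** The endpoints are timed after surgery ("Time Frame: 3 years postoperatively"), and section 3.4 names no path for mrTRG 1. The time origin and event definitions are commonly settled in an analysis plan, which is not shown here. The mrTRG 1 gap is a missing clinical detail. Neither is part of this point.

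**What to change.** In section 3.4:

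1. Delete the final clause of the experimental-arm sentence, the one that removes mrTRG 5 patients from the trial.
2. Keep immediate surgery for them, followed by postoperative treatment set by the clinical team. One option is adjuvant chemotherapy as in the control arm, allowing for cycles already given.
3. State that every randomised patient, whatever the mrTRG grade, stays in follow-up and in the primary analysis in the allocated arm.

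No extra patients are needed. The cost is standard follow-up of about 2 to 6 experimental patients (42 × 5% to 42 × 15%, an assumed share) and a written postoperative plan for them. The trade-off is one of interpretation: the retained patients will have had only part of the consolidation, so the result compares treatment strategies rather than completed courses.
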